#### **10.1.4 Dose Selection**

Dose selection for the further development will be based on the following efficacy and safety considerations; more than 1 dose may meet these criteria. An effective dose, or dose regimen, will be one that achieves clinically-meaningful reduction in plasma Lp(a) levels. Safety will be evaluated on the basis of incidence of expected and unexpected treatment-related SAEs and other specific safety considerations including the incidence of platelet reductions, and renal or hepatic injury.

#### **10.2 Sample Size Considerations**

Based upon prior clinical trial experience with ISIS 681257, it is estimated that the standard deviation of the percent change in Lp(a) is approximately 20%. With 23 patients in each ISIS 681257 treatment group and 23 in placebo group there would be approximately 90% power to detect a 20% difference in percent change in Lp(a) levels between the ISIS 681257 treatment groups and placebo group at an alpha level of 0.05, assuming 30% reduction in the ISIS 681257 patients and 10% reduction in the placebo patients.

Based upon prior clinical trial experience with Ionis ASOs, assuming the incidence rate of platelet count below lower limit of normal (LLN) in placebo treated patients is 1.9%, in the ISIS 681257 treated patients is 3.8%, twice the incidence rate observed in placebo, with 45 patients in each ISIS 681257 treatment group, there would be approximately 80% power to detect at least 1 event.

Therefore, approximately 270 patients (54 patients per cohort, including 45 patients per cohort treated with ISIS 681257) will be randomized to ensure that both the safety and efficacy of ISIS 681257 will be adequately characterized in the study.

#### **10.3 Analysis Populations**

Full Analysis Set (FAS): All patients who are randomized, received at least 1 dose of Study Drug (ISIS 681257 or placebo), and have a Baseline Lp(a) assessment. The FAS represents the practically-feasible intent-to-treat (ITT) population as delineated in ICH Guideline E9. This population will be used for the primary analysis of efficacy.

Per Protocol Set (PPS): Subset of the FAS who received within 6 months at least 5 monthly doses of Study Drug for patients randomized in Cohorts A, B, and C or at least 11 biweekly doses for patients randomized in Cohort D or at least 22 weekly doses for patients randomized in Cohort E, and who have no major protocol violations that could compromise the interpretation of efficacy. Major violations will be determined prior to unblinding for statistical analysis. This population will be used for supportive inferences concerning efficacy.

Safety Set: All patients who are randomized and receive at least 1 dose of Study Drug. This population will be used for all safety analyses.

PK Population: All patients who are randomized and received at least 1 dose of Study Drug, and have sufficient data for the analysis of PK parameters. This population will be used for analysis of PK data.

#### **10.4 Definition of Baseline**

Baseline for Lp(a), LDL-C, apoB, OxPL-apo(a), OxPL-apoB, and other lipid measurements will be defined the pre-dose measurement on Day 1 or closest to Day 1, prior to administration of Study Drug. The baseline for other measurements is defined as the last non-missing assessment prior to the first dose of Study Drug.

#### **10.5 Interim Analysis**

No interim efficacy analysis will be performed.

#### **10.6 Planned Methods of Analysis**

Summary tabulations will be provided for disposition, demographic, baseline, efficacy, and safety data as noted in the following sections. Hypothesis testing will be used for the primary efficacy endpoint and select secondary efficacy endpoints.

All eCRF data, lab data transfers, and any outcomes derived from the data will be provided in the patient data listings. Patient data listings will be presented for all patients enrolled into the study. Descriptive summary statistics including n, mean, median, standard deviation, standard error, interquartile range (25th percentile, 75th percentile), and range (minimum, maximum) for continuous variables, and counts and percentages for categorical variables will be used to summarize most data. Where appropriate, p-values will be reported. All statistical tests will be conducted using 2-sided tests with 5% Type I error rate unless otherwise stated.

##### ***10.6.1 Demographic and Baseline Characteristics***

Demographic and Baseline characteristics will be summarized using descriptive statistics by treatment group. The patient disposition will be summarized by treatment group. All patients enrolled will be included in a summary of patient disposition.

##### ***10.6.2 Safety Analysis***

###### ***10.6.2.1 Adverse Events***

Treatment duration and amount of Study Drug (ISIS 681257 or placebo) received will be summarized by treatment group. Patient incidence rates of all AEs will be tabulated by MedDRA system organ class, and

by MedDRA preferred term. Narratives of treatment-emergent deaths, serious and significant AEs, including early withdrawals due to AEs, will also be provided.

All treatment-emergent AEs, all treatment-emergent AEs potentially related to Study Drug, all treatment-emergent serious AEs, and all treatment-emergent serious AEs potentially related to Study Drug (ISIS 681257 or placebo) will be summarized.

#### **10.6.2.2 Clinical Laboratory Data**

Laboratory tests to ensure patient safety including chemistry panel, complete blood count (CBC) with differential, coagulation panel, complement, etc., will be summarized by study visits for each treatment group. These safety variables will also be presented as change and percent change from baseline over time after Study Drug (ISIS 681257 or placebo) administration, as appropriate. In addition, the number of patients who experience abnormalities in clinical laboratory evaluations will be summarized by treatment group.

#### **10.6.2.3 Vital Signs and Examinations**

Vital sign and ECG measures will be tabulated by treatment group.

### **10.6.3 Efficacy Analysis**

#### **10.6.3.1 Analysis of Primary Efficacy Endpoint**

The primary analysis of the primary endpoint will be the pairwise comparison of percent change from baseline to primary analysis time point in fasting Lp(a) between ISIS 681257 treatment groups and pooled placebo group in the FAS. The data will be analyzed using an analysis of covariance (ANCOVA) model with the Baseline Lp(a) as a covariate. Missing data may be handled by LOCF or multiple imputation methods ([Schafer 1997](#); [Schafer 1999](#)).

The primary efficacy analysis will take place after the last patient has completed the primary analysis time point, and the database has been locked,

The following sensitivity analyses will be conducted:

- The primary analysis will be repeated in the PPS
- The primary efficacy endpoint will be analyzed using a Wilcoxon Rank Sum test on both FAS and PPS, and the treatment effect will be estimated using Hodges-Lehmann estimator

Additional sensitivity analyses may be conducted as appropriate; the details of these analyses will be outlined in the SAP.

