increased proportionally with dose at dose levels ranging from 10 to 40 mg, and greater than dose proportionally at dose levels ranging from 40 to 120 mg.

After reaching  $C_{max}$ , mean plasma concentrations of ISIS 681257 declined in a biphasic fashion over time, with an initial, relatively fast distribution phase that dominated the plasma clearance followed by a slower elimination phase. Characterization of the terminal elimination phase yielded an apparent terminal elimination half-life of approximately 3 to 4 weeks over a dose range of 10 to 120 mg (either single- or multiple-dose), and appeared to be independent of dose. This result is consistent with the slow elimination of ISIS 681257 observed from monkey tissues, and the comparatively long elimination half-lives observed for this chemical class.

Plasma trough concentrations (168 hours or 7 days from previous dose) monitored during the treatment period in the multiple-dose cohorts increased with increasing dose, consistent with expectations (based on preclinical assessments and experience with other compounds of this chemical class) that trough plasma concentrations reflect exposure in tissues. Plasma trough concentrations did not increase greatly after the loading period (Day 15), suggesting that accumulation in major tissues of distribution had approached steady-state after the loading period.

Overall, the human PK of ISIS 681257 are consistent with the expected PK for compounds within this chemical class.

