### **8.8.1 *Follow-up Visits for Early Termination from Treatment Period or from Post-Treatment Follow-up Period***

Any patient who discontinues early from the treatment period or from post-treatment follow-up period should be followed as per the platelet monitoring rules shown in [Table 3, Section 8.6.3](#) for the first 6 weeks post treatment period. Following this period, if the platelet count is stable (at least 3 consecutive values that are stable as determined by the Sponsor Medical Monitor and  $> 100,000/\text{mm}^3$ ), platelets should be tested 10 and 16 weeks post treatment period (as per visit schedule).

If a patient early terminates from the treatment period, an ET visit (Week 53 visit assessments) should be performed at the time of withdrawal, and ideally within 2 weeks from the last dose of Study Drug, and patients should start the 16-week post-treatment follow-up period to collect the study assessments in accordance with the Schedule of Procedures in [Appendix A](#).

If the patient early terminates from the post-treatment follow-up period, a final visit (assessments from the Week 16 of post-treatment follow-up period) should be performed at the time of withdrawal.

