### **8.12 Safety Monitoring Compliance**

Compliance with safety monitoring requirements and treatment stopping rules must be documented by the Study Center staff.

Patients and the Study Investigators are required to adhere to a strict program of monitoring of platelet count, and liver and renal function as described in [Section 6.2.1](#), [Sections 8.5.1-8.5.3](#), and [Sections 8.6.1-8.6.3](#).

While on treatment patients will be required to have platelet counts every 2 weeks for the duration of the study and must not receive Study Drug without an interpretable platelet count result in the prior 2 weeks, in which case the Investigator must contact the patient to hold dosing until a new platelet count is obtained and reviewed, and will document this contact.

While on treatment patients will also be required to have renal function testing and assessment of biomarkers of renal damage every 2 weeks, and must not receive Study Drug if there are no test results for parameters considered critical to patient safety available within the prior 2 weeks. In such a case, the Investigator must contact the patient to hold dosing until these or new tests are obtained and reviewed.

Adherence to the program will be closely monitored by the Sponsor, and patients and trial sites that are unable or unwilling to comply with this important risk mitigation program will be discontinued from the study.

Patients should be informed of the possibility and risks of a reduction in platelet count, and of potential hepatic and renal risks, and the importance of adherence to the monitoring program. Any case of a platelet count reduction to levels below 50,000/mm^3 (Grade 3 or Grade 4), or any event meeting renal stopping rules criteria described in [Section 8.6.2](#) are considered adverse events of special interest and should be reported in an expedited fashion to the Sponsor.

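### Patients who stop study drug early usually have no Lp(a) sample at Week 25/27, and the protocol permits LOCF there without saying which values may be carried

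*Protocol*

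**What the plan says.** References are to the current protocol (Amendment 6); the SAP is not shown.

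The primary endpoint is the percent change in fasting Lp(a) from baseline at Week 25 (Cohorts A-C) or Week 27 (D, E), analysed by ANCOVA in the FAS. The FAS takes every randomised patient with at least one dose and a baseline Lp(a). Section 10.3 adds: "The FAS represents the practically-feasible intent-to-treat (ITT) population as delineated in ICH Guideline E9". On missing values, 10.6.3.1 says "Missing data may be handled by LOCF or multiple imputation methods". It names two sensitivity analyses: a repeat in the PPS, and a Wilcoxon test with a Hodges-Lehmann estimate.

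For a patient who stops treatment early, 8.8.1 asks for an ET visit at withdrawal, preferably no more than 2 weeks after the last dose. After that, "patients should start the 16-week post-treatment follow-up period to collect the study assessments in accordance with the Schedule of Procedures". Section 8.5 sends patients with a confirmed stopping criterion the same way. Follow-up visits fall 4, 10 and 16 weeks after the treatment period (3.4.3), which ends one dosing interval after the last dose (6.1.2).

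Appendix A schedules the PD panel, which contains Lp(a), during follow-up. For D and E it is drawn at all three visits. For A-C, as the table reads here, it is drawn at 10 and 16 weeks; the blank at 4 weeks may be a text-extraction fault.

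Two provisions can end participation without follow-up. Section 8.9 withdraws patients from the study (for example for noncompliance) and asks only for the ET assessments. Section 8.12 says that "patients and trial sites that are unable or unwilling to comply with this important risk mitigation program will be discontinued from the study".

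Section 2.3.4 reports an "apparent terminal elimination half-life of approximately 3 to 4 weeks".

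**The concern.** The schedule and the analysis do not meet. The analysis needs a Week 25/27 value for every FAS patient, but nothing brings an early stopper back at that time. The off-drug samples that do exist in follow-up are not assigned to it. A SAP can choose an imputation method, but it cannot create a sample that was never drawn.

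LOCF is named as acceptable for the primary analysis. A SAP that carries forward the ET value would therefore comply with the protocol, although that value is taken within about one dosing interval of the last dose. Neither named sensitivity analysis varies the missing-data handling. The PPS removes most early stoppers through its minimum dose counts, and the Wilcoxon analysis changes the test.

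What is at stake is the size of the estimate. Section 10.1.4 defines an effective regimen by a clinically meaningful Lp(a) reduction. Section 2.4 predicts reductions of about 60% to 85% over four exposure levels. If these were evenly spaced (an assumption), one step would be (85 - 60)/3 = 8.3 points, so an error of a few points in one arm could matter when regimens are compared.

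**Working it through.** **1. The plan's own figure.** Inputs from 10.2 and 10.6: difference 20 points, SD 20, 23 per group, "at an alpha level of 0.05", and "All statistical tests will be conducted using 2-sided tests with 5% Type I error rate". The normal approximation gives n = 2 x (1.960 + 1.282)^2 x (20/20)^2 = 21.0, so 22 per group. A two-sided t test with 23 v 23 has power 0.912. This agrees with the stated "approximately 90% power to detect a 20% difference in percent change in Lp(a) levels". Section 10.2 gives no dropout rate.

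**2. Does a follow-up visit fall on Week 25/27?** End of treatment = last-dose week + dosing interval (1 week in E, 2 in D, 4 in A-C). Follow-up = end + 4, + 10, + 16. The visit window is 3 days either way, so only an exact week counts.

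| Cohort | Last-dose weeks with treatment ending before the primary visit | Follow-up Lp(a) at the primary week |
|---|---|---|
| E | 1 to 25 (25 dates) | 3 (last dose Week 10, 16 or 22) |
| D | 1, 3, ... 23 (12 dates) | 3 (Week 9, 15 or 21) |
| A-C, with a 4-week sample | 1, 5, 9, 13, 17 (5 dates) | 2 (Week 5 or 17) |
| A-C, as the table reads | same 5 dates | 1 (Week 5) |

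**3. If LOCF uses only treatment-period or ET values, or follow-up is missed.** The longest carry is for a last dose at Week 1.
- E: 27 - 2 = 25 weeks; D: 27 - 3 = 24 weeks; A-C: 25 - 5 = 20 weeks.
- Time since last dose is 26 weeks (D, E) or 24 weeks (A-C). In half-lives: 26/4 = 6.5 to 26/3 = 8.7, and 24/4 = 6 to 24/3 = 8.

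**4. If LOCF may use follow-up values and visits are attended.**
- E: off-drug value for 22 of 25 dates. D: 11 of 12. The others carry the ET value for 1 to 3 weeks, with 0.5 to 1.3 half-lives since the last dose.
- A-C as the table reads: 3 of 5. Last doses at Week 13 and 17 carry the ET value for 8 and 4 weeks, with Week 25 falling 2 to 4 half-lives after the last dose. With a 4-week sample: 5 of 5.

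**5. Size under step 3.** Overstatement = d x effect x (1 - r), where d is the share stopping early and r the share of effect left at Week 25/27. The values of d are assumed. Effects against placebo use the 10% placebo reduction in 10.2: 30 - 10 = 20, 60 - 10 = 50, 85 - 10 = 75.

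| Effect (points), r = 0 | d = 5% | d = 10% | d = 20% |
|---|---|---|---|
| 20 | 1 | 2 | 4 |
| 50 | 2.5 | 5 | 10 |
| 75 | 3.8 | 7.5 | 15 |

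With r = 0.5 each entry halves.

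**6. Power if off-drug values are used.** At the planned 45 v 45 and a 20-point difference, power is 0.997. With d = 20% and full washout the difference is 20 x 0.8 = 16 and power is 0.964. Allowing for the mixture of patients, the active SD is sqrt(20^2 + 0.2 x 0.8 x 20^2) = 21.5 and power is about 0.95.

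**The case against.** Most of the opposing case limits the size of the problem; it does not remove it.

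- **The SAP settles data handling.** Section 10 leaves data-handling conventions to the SAP, and 10.6.3.1 leaves it any further sensitivity analyses. The SAP may choose multiple imputation or allow follow-up values. That stands for the method. It does not stand for the missing sample, which depends on the visit schedule.
- **Off-drug Lp(a) is collected.** This stands. A reader might infer that every early stopper lacks a primary value, or that LOCF must carry an on-drug value past washout. Steps 2 and 4 show neither is so. Patients whose treatment ends before Week 9 (A-C) or Week 11 (D, E) finish follow-up before the primary visit. Their last scheduled sample is nevertheless 17 to 20 weeks after the last dose, which is 17/4 = 4.3 to 20/3 = 6.7 half-lives.
- **The sizes are upper bounds.** This stands. The 60% to 85% reductions are steady-state predictions. With a 3 to 4 week half-life, reaching 90% of steady state takes about 10 to 13 weeks and 90% washout takes as long again. Together that is 20 to 27 weeks, so a full carried effect and a full washout fit only a narrow range of stop dates. Section 10.2 assumes that only 3.8% of active patients fall below the platelet LLN, and the permanent platelet stop needs a much lower count. Platelet stops alone should therefore be rare.
- **Stopping related to dose.** A reader might infer that bias must differ between arms because stopping is triggered by safety rules. It may, but the protocol does not show it. Section 2.3.4 reports that Phase 1 platelet changes did not appear dose related.
- **The PPS already helps.** In part. It shows how far the result depends on early stoppers, but by excluding them.
- **Stopping drug and leaving the study.** A reader might infer that the protocol confuses the two. Sections 8.8 and 8.9 treat them separately, and 8.5 keeps stopping-rule patients in follow-up, so 8.9 needs no change.

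**Conclusion.** The point holds in a limited form. Most early stoppers have no Lp(a) sample at the primary time point, their off-drug samples are not assigned to it, and LOCF is permitted without a rule on which values may be carried. An analysis that complies with the protocol could therefore enter on-drug values long after the last dose into a set described as ITT.

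The ranges in step 5 are upper bounds. They rest on assumed stopping rates of 5% to 20%, full washout, and carrying only treatment-period or ET values. Washout is judged from the plasma half-life because the protocol gives no Lp(a) recovery rate. The overstatement is smaller if follow-up values are used or some effect remains.

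A reader might infer that the efficacy conclusion or the sample size is in danger. Neither is: power stays at about 0.95 or above at 45 v 45 even with 20% stopping. The issue is bias in the effect size that feeds dose selection. It is worth correcting because it is cheap and an undrawn sample cannot be recovered, but it does not undermine the trial.

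**What to change.** 1. In 8.8.1 and Appendix A, keep the nominal Week 25 (A-C) or Week 27 (D, E) fasting Lp(a) sample for every patient who stops study drug early and has not withdrawn consent. Use that value in the FAS analysis.
2. In 10.6.3.1, remove LOCF as a primary option and name multiple imputation as the single primary method. Values after drug stop should be imputed using observed off-drug follow-up Lp(a). Placebo-based imputation can be a sensitivity analysis only.

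The cost is a short amendment with matching SAP text, and one extra blood draw per early discontinuer: about 27 draws if 10% of 270 stop (assumed). The sample size does not change.

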#### **10.6.3.2 Analysis of Secondary Efficacy Endpoints**

- Percent change from baseline at the primary analysis time point in fasting LDL-C will be compared between each ISIS 681257 treatment groups and pooled placebo group using an ANCOVA model with baseline as covariate

- Proportion of patients who achieve  $\leq 50$  mg/dL ( $\leq 125$  nmol/L) in fasting Lp(a) at the primary analysis time point will be compared between each ISIS 681257 treatment group and pooled placebo group using a logistic regression model with Baseline Lp(a) as a covariate. Proportion of patients who achieve  $\leq 30$  mg/dL ( $\leq 75$  nmol/L) in fasting Lp(a) at the primary analysis time point will be analyzed similarly
- Percent change from baseline at the primary analysis time point in fasting apoB, OxPL-apo(a) and OxPL-apoB will be compared between ISIS 681257 treatment groups and pooled placebo group using an ANCOVA model with baseline as covariate

All analyses of secondary endpoints will be performed on the FAS as primary and PPS as supportive.

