### **8.6 Stopping Rules**

For the purposes of stopping rules, Baseline is defined as the average of Day 1 pre-dose assessment and the last measurement prior to Day 1.

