### Appendix A Schedule of Procedures – Weekly and Every 2 Week Dosing Continued

- j Blood samples to be collected after an overnight fast of at least 10 hours and preferably not more than 12 hours, unless tests are repeated for safety reasons.
- k If the platelet value, serum creatinine or liver enzyme tests are uninterpretable (e.g., due to clumping, hemolysis or quantity not sufficient) a repeat blood specimen should be re-drawn as soon as possible (ideally within 7 days). All platelet count results will be reviewed promptly (within 24 hours of receipt) by the Investigator as per [Section 6.2.1](#). Any case of a platelet count  $< 50,000/\text{mm}^3$  should be reported in an expedited fashion to the Sponsor.
- l Refer to [Appendix C](#) for PK Sampling schedule.
- m Women who are not surgically sterile or post-menopausal.
- n Serum and plasma samples will be collected and stored for follow-up exploration of laboratory findings and/or AEs (e.g., measurement of cytokine and/or chemokine levels, measurement of additional markers of kidney function, measurement of antibodies, etc.) and will be retained until completion of the final study report.
- o Patients will continue treatment in the study for 12 months, or until the last patient reaches 6 months of exposure. When this milestone is met, all patients still on treatment will have an End of Treatment visit, then enter a 16-week post-treatment follow-up period.
- p For the last patient to reach 6 months of exposure ONLY, the Week 27 visit will count as the End of Treatment Visit, therefore all Week 53/ET assessments will be included in this visit. No dose will be administered at this visit.

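### The efficacy ANCOVAs are valid but name one pre-dose covariate; adding the Screening value already collected could sharpen the LDL-C and apoB comparisons at almost no cost

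*Protocol*

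**What the plan says.** Section 10.4 defines the efficacy baseline for Lp(a), LDL-C, apoB, OxPL-apo(a) and OxPL-apoB as "the pre-dose measurement on Day 1 or closest to Day 1, prior to administration of Study Drug". That is one value per patient.

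Section 10.6.3.1 says of the primary comparison: "The data will be analyzed using an analysis of covariance (ANCOVA) model with the Baseline Lp(a) as a covariate". In section 10.6.3.2, percent change in LDL-C "will be compared between each ISIS 681257 treatment groups and pooled placebo group using an ANCOVA model with baseline as covariate", and percent change in apoB, OxPL-apo(a) and OxPL-apoB "will be compared between ISIS 681257 treatment groups and pooled placebo group using an ANCOVA model with baseline as covariate". No other covariate is named.

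Both Appendix A schedules (weekly and every-2-week dosing; every-4-week dosing) mark the PD panel and the lipid panel at Screening and again on Day 1. Both rows carry the fasting footnote: "Blood samples to be collected after an overnight fast of at least 10 hours and preferably not more than 12 hours". Appendix B places Lp(a) and the two OxPL measures in the PD panel, and LDL-C and apoB in the lipid panel. A second fasting pre-dose value is therefore scheduled for every ANCOVA endpoint.

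Elsewhere the protocol does use two pre-dose values. For the stopping rules in section 8.6, "Baseline is defined as the average of Day 1 pre-dose assessment and the last measurement prior to Day 1", and section 8.5 does much the same for safety monitoring.

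**The concern.** Each endpoint is a percent change from Day 1, so chance variation in the Day 1 value enters the outcome through its denominator. Adjusting for Day 1 takes out part of that variation. The Screening value carries further information on whether Day 1 was unusually high or low for that patient. It should be comparable with Day 1, since section 5.1 requires lipid-lowering drugs to be stable for at least 4 weeks before Screening. Leaving it out of the model can make confidence intervals wider than the collected data require.

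The stake is largest for LDL-C and apoB. Section 10.2 gives efficacy power for Lp(a) only, and each secondary comparison rests on 45 active against 45 pooled placebo patients (sections 3.1 and 10.2).

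**Working it through.** **Plan's own figure.** Section 10.2 uses SD 20%, a 20-point difference, 23 versus 23 and two-sided alpha 0.05. The noncentrality is 20 / (20 × √(2/23)) = 3.39 on 44 df, and the t-test power is 91.2%, against the stated figure of approximately 90%. It reproduces. At the actual 45 versus 45, the noncentrality is 20 / (20 × √(2/45)) = 4.74 on 88 df, and power is 99.7%. The primary comparison has nothing useful to gain.

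**Variance ratio, two pre-dose covariates against one (assumed correlations).** Let a be the correlation of Day 1 with the primary visit, b that of Screening with the primary visit, and c that of Screening with Day 1. The residual variance, as a fraction of the visit variance, is 1 − a² with Day 1 alone and 1 − (a² + b² − 2abc)/(1 − c²) with both.

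If all three correlations equal r, the ratio simplifies to (1 + 2r)/(1 + r)²:

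- r = 0.3: 1.6/1.69 = 0.947
- r = 0.5: 2.0/2.25 = 0.889
- r = 0.7: 2.4/2.89 = 0.830
- r = 0.8: 2.6/3.24 = 0.802
- r = 0.9: 2.8/3.61 = 0.776

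Equal correlations are the favourable case. Screening falls within 4 weeks of Day 1, while the primary visit is Day 169 or Day 183, so c may well exceed a and b:

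- (a, b, c) = (0.7, 0.7, 0.8): residual 1 − 0.196/0.36 = 0.456 against 0.510, ratio 0.893
- (0.7, 0.65, 0.8): 0.4875/0.510 = 0.956
- (0.7, 0.56, 0.8), where correlation simply decays with time so that b = a × c: 0.510/0.510 = 1.00, no gain

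**Percent change as the outcome.** The formulas above apply to a linear outcome, so the actual endpoint type was simulated at 45 versus 45. Assumptions: log-normal values, equal correlation r, CV 30% and a true 10% reduction. There were 6,000 trials per setting.

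| r | Variance ratio | Estimate, Day 1 only | Estimate, Day 1 + Screening |
|---|---|---|---|
| 0.5 | 0.926 | −10.39 | −10.40 |
| 0.7 | 0.862 | −10.23 | −10.25 |
| 0.8 | 0.836 | −10.27 | −10.23 |
| 0.9 | 0.808 | −10.11 | −10.09 |

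The two estimates agree within 0.04 points. A second simulation used a 12% reduction, between-person log SD 0.3 to 0.4, within-person log SD 0.08 to 0.12 and response SD 0 or 0.15. It gave ratios of 0.80 to 0.90, or 0.91 to 0.95 with an added long-term drift SD of 0.15.

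**Large-effect endpoint.** With a 75% reduction, CV 50% and r = 0.8, 0.9 and 0.95, the ratio is 0.906, 0.935 and 0.956 when response varies between patients (log SD 0.5). It is 0.914, 0.870 and 0.859 when response is constant. At r = 0.8 and 0.9 both are weaker gains than in the small-effect table.

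**What the ratio buys.** A ratio of 0.80 makes 45 patients act like 45/0.80 = 56 and shrinks the standard error by the factor √0.80 = 0.894. A comparison that has 80% power at 45 versus 45 would have about 82% at ratio 0.95, about 88% at 0.80, and still 80% at 1.00. This holds for any SD.

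**The case against.** The case against is substantial. ANCOVA on a single pre-dose baseline is a standard, valid analysis, and nothing in the protocol is contradicted. Section 10 leaves additional methods to the SAP, which is not shown, and naming one covariate does not forbid a second. Dose selection (section 10.1.4) rests on Lp(a) reduction and safety, so no decision turns on LDL-C or apoB precision. All of this stands, and it limits the point to an efficiency suggestion.

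A reader might infer more than the documents support:

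- **That Day 1 error is untouched by the planned model.** It is partly removed. With equal correlation 0.8, an unadjusted change has variance 2(1 − 0.8) = 0.40, adjusting for Day 1 gives 1 − 0.64 = 0.36, and adding Screening gives 0.289.
- **That the Screening value is thrown away.** Section 10.4 accepts the pre-dose value closest to Day 1, so Screening is the fallback when Day 1 is missing.
- **That some gain is guaranteed.** It can be zero, as the decay pattern shows.
- **That the OxPL endpoints lose as much as LDL-C.** Section 2.1.2 says OxPL-apoB largely reflects OxPL on Lp(a), and section 2.4 predicts Lp(a) reductions of about 60% to 85%. A large OxPL effect is therefore plausible, and precision matters less.
- **That the gain can be stated in percentage points of LDL-C or apoB.** Section 10.2 says "it is estimated that the standard deviation of the percent change in Lp(a) is approximately 20" (per cent), which is for Lp(a) only. The documents give no SD for any secondary endpoint, so a detectable difference built on 20% says nothing about them.

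**Conclusion.** The point holds as a nearly cost-free improvement, not as an error in the plan. Two fasting pre-dose values are scheduled for every ANCOVA endpoint and the models name one. Using both would reduce the variance of the treatment effect by about 0% to 20%, which narrows confidence intervals by 0% to about 11%, without bias. The upper end needs Screening to predict the primary visit about as well as Day 1 does. The lower end applies if correlation decays with time. The documents contain no correlation that would place the trial within this range.

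The benefit lies mainly with LDL-C and apoB. It is immaterial for primary Lp(a) and likely smaller for OxPL.

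**What to change.** Leave the endpoint definitions and the Day 1 baseline of section 10.4 as they are. Before unblinding, state in the SAP, and align section 10.6.3.2 with it, that the ANCOVAs for LDL-C and apoB include the same analyte's Screening value as a second covariate. The Lp(a) and OxPL models may follow for consistency.

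Two rules are needed:

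- **Which Screening value.** Section 6.1.1 allows one retest of abnormal results and one re-screening. Use the last scheduled Screening value before Day 1 from the screening episode that led to randomization.
- **Fallback and missing values.** Where Screening itself serves as the baseline, the second covariate would duplicate the first. In that case, and where Screening is missing, fill the missing pre-dose value by a simple imputation that ignores treatment group.

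Use the Screening value as a covariate and do not average it into the baseline. Averaging gave somewhat larger gains in the 10% simulation (ratios 0.84 to 0.77), but it changes the endpoint. For Lp(a), if the 60 mg/dL entry criterion is judged at Screening, averaging would also bring regression to the mean into the within-group percent changes.

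The cost is a few sentences and one degree of freedom per model, with no new sampling.
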